Appendix A: Parameters

Sampling will be done for every dialysis treatment (3 times per dialyzer, per patient)

Performance		60 min	
Clearance	Urea	V, A	
63	Phosphate	V, A	
63	Creatinine	V, A	
"	ß2-m	V, A	
"	Myoglobin	V, A	

ĪĒ

XVenous sampling will be first, followed by the arterial

%Do not adopt "slow flow sampling method".

Performance	pre	240 min
Removal Rate Urea	А	А
" Phosphate	А	А
" Creatinine	А	А
" ß2-m	А	А
" Myoglobin	А	А

Sampling will be done once per patient, per dialyzer

Hemocompatibility	Pre	15 min	30 min	60 min	240 min
WBC	А	А	А	А	А
Platelet Count	А	А	А	А	А
Hb / Hct	А	А	А	А	А
C5a	А	А	А	А	А
ТАТ	А			А	А

A Clinical Study Comparing The Basic Performance and Blood Compatibility Characteristics of Nipro ELISIO-H, Gambro Polyflux Revaclear, and Fresenius Optiflux Artificial Kidneys

	Residual blood behaviour					*)
--	--------------------------	--	--	--	--	----

A: arterial sample (= pre-dialyzer)

V: venous sample (= post-dialyzer)

*) visual evaluation after intensive rinsing

Appendix B: Blood Volumes

Monday Wednwsday Friday Clearence Studies 84 cc/wk						
	Pre	60' A	60' V	Post		
Monday	7 cc SST	7 cc SST	7 cc SST	7 cc SST	28 cc/day	
Wednesday	7 cc SST	7 cc SST	7 cc SST	7 cc SST	28 cc/day	
Friday	7 cc SST	7 cc SST	7 cc SST	7 cc SST	28 cc/day	

	Wednes	Wednesday Compatibility Studies			vk
	Pre	15'	30'	60'	Post
CBC	2 cc Lavr	2 cc Lav	2 cc Lav	2 cc Lav	2 cc Lav
10 cc/day	,				
C5a	3 cc Lav	3 cc Lav	3 cc Lav	3 cc Lav	3 cc Lav
15 cc/day	,				
TAT	4.5 cc Lt Blue	4.5 cc Lt Blue	4.5 cc Lt Blue	4.5 cc Lt Blue	4.5 cc Lt Blue
22.5 cc/da	ау				

Total blood volume = 131.5 ml/week x 3 weeks = 394.5 ml/Patient

DCI Corporate Epogen Management Protocol

- 1) The goal of the protocol is to maintain Hgb at 11-12 g/dl. Erythropoietin doses are to be based upon the estimated dry weight.
- 2) The protocol will change the erythropoietin dose no more often than every 4 weeks except in the following cases:
 - a. Discontinue erythropoietin when Hgb is greater than 13 g/dl.
 - b. Increase the erythropoietin dose when Hgb is less than 11 g/dl and the previous dose change was a reduction in erythropoietin.
 - c. Decrease erythropoietin dose based upon rules 8g-8i when Hgb is between 12-13 g/dl.
 - d. Increase erythropoietin according to rule 8a when Hgb decreased from above 10 g/dl to below 10 g/dl.
- 3) If Hgb is greater than 13 g/dl then discontinue erythropoietin and check Hgb weekly. Resume erythropoietin at 25% less than the previous dose as soon as the Hgb is below 12.5 g/dl. If Hgb remains higher than 12.5 g/dl for more than three months return to the clinic's policy of testing Hgb.
- 4) For established patients who have had not had an erythropoietin within the last 3 months and have a Hgb <11 g/dl start erythropoietin at 300 units/kg/week; for a Hgb of 11-11.9 start erythropoietin at 150 units/kg/week.
- 5) For new patients without erythropoietin orders who have a Hgb <11 g/dl start erythropoietin 300 units/kg/week; for a Hgb of 11-11.9 start erythropoietin at 150 units/kg/week; for those with a Hgb > 11.9 g/dl do not start erythropoietin.
- 6) The weekly doses described in number 4 and 5 above will be equally divided into IV dosing for each HD treatment and will be given SQ as a single weekly dose for PD patients.
- 7) Increase erythropoietin dose by protocol no higher than 900 units/kg/week or 400,000 units per month.
- 8) For patients who have an erythropoietin (EPO) order and the order was not changed within the last 4 weeks or cases described in Number 2 above:
 - a. If Hgb < 10 g/dl then increase EPO 50% but not less than 300 unites/kg/week.

- b. If Hgb is between 10-10.9 then increase EPO 25% but not less than 75 units/kg/week.
- c. If Hgb is between 11-11.9 and Hgb has decreased 0.5 g/dl or more since last dose change then increase EPO 10%.
- d. If Hgb is between 11-11.9 and Hgb has increased/decreased 0.5 g/dl since last dose change then do not change EOP dose.
- e. If Hgb is between 11-11.7 and Hgb increased0.5 g/dl or more since last dose change then do not change EPO dose.
- f. If Hgb is between 11.8-11.9 and Hgb increased 0.5 g/dl since last dose then decrease EPO dose by 10%.
- g. If Hgb is between 12-12.4 g/dl and Hgb decreased 0.5 g/dl or more since last dose change do not change EPO dose and check Hgb in 2 weeks.
- h. If Hgb is between 12-12.4 and Hgb increased/decreased less than 0.5 g/dl since last dose change then decrease EPO 10% and check Hgb in 2 weeks.
- i. If Hgb is between 12-12.4 g/dl and increased 0.5 g/dl or more since last dose change then decrease EPO 25% and check Hgb in 2 weeks.
- j. If Hgb is between 12.5-13 g/dl and Hgb decreased 0.5 g/dl or more since last dose change then decrease EPO 10% and check Hgb in two weeks.
- k. If Hgb is between 12.5-13 g/dl and Hgb increased/decreased less than 0.5 g/dl since last dose change then decrease EPO 25% and check Hgb in 2 weeks.
- If Hgb is between 12.5-13 g/dl and Hgb increased 0.5 g/dl or more since last dose change decrease EPO 25% and check Hgb weekly.
- m. If Hgb is greater than 13 then stop EPO and check weekly.
- 9) All erythropoietin dose decreases will be rounded to the nearest 200 units. All erythropoietin dose increases will be rounded up to the nearest 200 units. Dose will not be decreased below 400 unites.

Statistical Analysis Plan

For

A Clinical Study Comparing the Basic Performance and Blood Compatibility Characteristics of Nipro ELISIO-H, Gambro Polyflux Revaclear and Fresenius Optiflux Dialyzers

NCT02433210

July 23, 2019

Software:

Data were analyzed in house using SigmaPlot for Windows 11.2 (Systat Software, Inc., San Jose, CA, USA) for statistical analysis.

Methods:

Parametric non-paired t-test was used to compare groups except where the data failed the normality test or the variance test, then the nonparametric Mann–Whitney Rank Sum was utilized to test for significance.

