Ten (10) stable patients receiving regular dialysis treatment will be chosen for this evaluation. The n of ten was chosen from previous experience with studies of this kind. However with the expectation of a 20% drop out rate a total of twelve patients will be selected from the patient population meeting the inclusion criteria. Standard hemodialysis will be performed with each dialyzer type.

d) Patient Inclusion Criteria

- ESRD patients 18 years or older
- Stable on hemodialysis for more than 3 months
- Stable hemoglobin 11 g/dl or greater, see attached DCI erythropoietin protocol.
- Stable AV fistula vascular access
- Stable anticoagulation and ESA regimen

- No active infection
- Able to sign informed consent and able to participate in the study
- Medically stable

e) Patient Exclusion Criteria

- Participation in another study which may interfere with the planned study
- Active infection
- Medical conditions which may interfere with the study (cardiac, liver disease,
- Hepatitis)
- Female who are pregnant or planning to be pregnant
- Problem with or allergy to anticoagulation
- Patient cannot tolerate Heparin
- Allergy to dialyzer material e.g. polysulfone

f) Withdrawal Criteria

- Patients own decision.
- Relocation, transportation
- Severe mechanical problems with dialyzers e.g. frequent fiber leakages.
- Hypertensive reactions e.g. erythema, edema.
- Non-compliance with therapeutic regimen.
- Change of anticoagulation scheme.
- Other serious problems induced by treatment.
- Any dialysis-related medical problem judged to be sufficiently serious by the principal investigator to necessitate patient withdrawal.

1. Methods

a) Pre-rinsing of Dialyzers

Setting up and preparation of the dialyzers will be performed per the clinic's normal procedure. This involves a pre-rinsing step before the start of dialysis.. The priming solution will not be infused to the patient. Dialysate flow rate is to be initiated at the beginning of the rinsing procedure. All the dialyzers will be pre-rinsed in the same procedure.

b) Heparinization

The usual heparin type and dosage normally used for each individual patient, including the administration regime (bolus injection and continuous infusion), will be maintained

for each patient unless specified otherwise by the investigator/physician during the evaluation. The total amount of heparin given per treatment will be documented.

c) Blood Flow / Dialysate Flow

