Hemodialysis: Blood and dialysate flow rates should be between QB= 300 - 500 ml/min and QD= 2 times QB but should follow existing flow rates for the patient, based on clinic procedure. Blood flow and dialysate flow should remain unchanged for all patients for the duration of dialysis and throughout the evaluation. The ultrafiltration rate, appropriate for each patient and treatment will be maintained and recorded. The blood flow will also be determined in the fistula using a Doppler flow device.

d) Dialysis Regime and Number of Applied Dialyzers

Three consecutive treatments will be performed with each dialyzer type. Blood sampling for measurements will be taken as shown in appendix.

e) Performance and Hemocompatibility Parameters to be measured

Please refer to Appendix.

f) Blood Sampling

Blood will be collected pre-, during and post-dialysis at appropriate time intervals (see Appendix) for the evaluation of:

- Clearance of urea, creatinine, phosphate, beta-2-microglobulin, myoglobin at 60 min. Five minutes before the collection the flow rate will be adjusted so that at time of collection, QB= 350 mL/min, QD= 700 mL/min and UF= 0 for all patients. Blood is to be collected from venous side first followed by arterial side.
- 2. **Removal Rate** for urea, creatinine, phosphate, beta-2-m and myoglobin at 0 min and 240 min will be calculated.

3. Hemocompatibility

- (a) Blood cell count (white blood cell and platelet counts).
- (b) Hb / Hct.
- (c) C5a (activation of complement)
- (d) Thrombin-Antithrombin Complex (TAT)

The samples will be collected after confirming that the blood and dialysate flows are at the targeted rates listed above, venous and arterial pressure at point of collection are to be recorded as well. For blood volumes see appendix B.

g) Visual estimation of the amount of clotted capillaries

After dialysis removal of the residual blood is performed by means of ultrafiltration with reverse osmosis water from dialysate compartment to blood compartment (0.5-1 bar water pressure and the overall appearance of dialyzer will be photographed, with focus on the clotted fibers and any residual header blood. This will be carried out at the end of each treatment for each dialyzer (3 times each dialyzer). The number of clotted capillaries in the dialyzer are counted after removal of the plastic casing and classified by the following table.

	Number of clotted fibers							
	0 – 10 11 – 20 21 – 50 51 – 100 >100							
Score	1	2	3	4	5			

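### Every patient is treated with all three dialyzers, but the SAP compares dialyzers only with independent-samples tests, so the pairing within patients is ignored.

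*SAP*

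**What the plan says.** **Design.** The protocol (section c, Patients) seeks ten evaluable patients and states that "Standard hemodialysis will be performed with each dialyzer type". Section d of Methods (Dialysis Regime) adds: "Three consecutive treatments will be performed with each dialyzer type". No section describes separate patient groups. The word crossover is not used.

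**Measurements.** Appendix A sets the number of values per patient:
- Clearance and removal rate: "Sampling will be done for every dialysis treatment (3 times per dialyzer, per patient").
- Hemocompatibility: "Sampling will be done once per patient, per dialyzer". Within that one session there are five time points for white cells, platelets, Hb/Hct and C5a, and three for TAT.
- Clotting score (ordinal, 1 to 5): Methods section g says "This will be carried out at the end of each treatment for each dialyzer (3 times each dialyzer"), following the rinsing and photography step. In Appendix A the row "Residual blood behaviour" is printed after the once-per-dialyzer heading, although this may be only a layout effect.

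**Analysis.** The SAP Methods section is a single sentence: "Parametric non-paired t-test was used to compare groups except where the data failed the normality test or the variance test", in which case the Mann-Whitney rank sum test was used. It names no paired test, repeated-measures analysis, Friedman test or model with a patient effect. It is written in the past tense, so it reports an analysis already done.

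**The concern.** When the same patients contribute to both sides of a comparison, the variance of the difference depends on the correlation between a patient's values under the two dialyzers. An independent-samples test sets that correlation to zero. The p-values, and any confidence interval built on the same standard error, are then wrong in general.

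The aim is to compare ELISIO-H with two marketed dialyzers in about ten patients, and using each patient as his or her own control is the main strength of so small a study. With one value per patient and dialyzer and positive correlation, the unpaired test is conservative. Ignoring the pairing does not create false positives, but it can hide real differences between dialyzers, and a non-significant result may then be taken as evidence that they perform alike.

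Clearance and removal rate raise a further question. If the three sessions were entered as separate observations, repeated values from one patient were also counted as independent. That works in the opposite direction.

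**Working it through.** **1. Is the design within-patient?** Appendix B gives 3 × 28 = 84 ml per week for clearance studies and 10 + 15 + 22.5 = 47.5 ml for compatibility studies. The total is 131.5 ml per week; × 3 weeks = 394.5 ml per patient, as printed. Three sessions a week for three weeks is nine sessions per patient, that is, three on each of three dialyzers.

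**2. The plan's own sample-size figure.** 10 × 1.20 = 12, as stated; the alternative 10 / 0.80 = 12.5 rounds up to 13. The documents give no alpha, effect size, SD or correlation, so there is no power figure to reproduce. Below I assume a two-sided 5% level and normal data, and show rho as a range.

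**3. One value per patient and dialyzer.** With n patients and SD σ:
- True variance of the mean difference: 2σ²(1 − rho)/n
- Variance assumed by the unpaired test: 2σ²/n

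The unpaired standard error is therefore too large by 1/√(1 − rho): 1.20, 1.41 and 2.24 at rho 0.3, 0.5 and 0.8. Simulated type I error and power for a 1 SD difference:

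| rho | Type I, unpaired t (n=10) | Type I, Mann-Whitney (n=10) | Power, unpaired v paired t (n=10) | Power, unpaired v paired t (n=12) |
|---|---|---|---|---|
| 0 | 5.0% | 4.3% | 56% v 51% | 65% v 61% |
| 0.3 | 2.2% | 1.9% | 57% v 66% | 67% v 76% |
| 0.5 | 0.9% | 0.9% | 59% v 80% | 70% v 88% |
| 0.8 | <0.1% | <0.1% | 62% v 99% | 76% v >99% |

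The paired t-test holds about 5% throughout. For a smaller difference of 0.8 SD at rho 0.5 and n=10, power is 37% unpaired and 61% paired.

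**4. When does pairing stop helping?** A paired test has n − 1 degrees of freedom instead of 2n − 2. Equating the critical differences gives a break-even rho of 1 − (t(2n−2)/t(n−1))². For n=10 this is 1 − (2.101/2.262)² = 0.137; for n=12, 1 − (2.074/2.201)² = 0.112.

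**5. Clearance and removal rate, if 30 v 30 session values were entered.** Let P be the patient variance, PD the patient-by-dialyzer variance and S the session variance.
- True variance of the difference: 2(3PD + S)/(3n)
- Assumed variance: 2(P + PD + S)/(3n)
- Ratio: (3PD + S)/(P + PD + S), which exceeds 1 only if PD > P/2

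Simulated type I error for 10 patients, total variance 1:

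| PD/P | S = 0.2 | S = 0.4 | S = 0.6 |
|---|---|---|---|
| 0 | 0.1% | 0.5% | 1.5% |
| 0.2 | 2.3% | 2.7% | 3.4% |
| 0.4 | 5.2% | 4.9% | 4.9% |
| 0.5 | 6.7% | 6.1% | 5.5% |
| 1 | 11% | 10% | 8% |
| 4 | 19% | 16% | 12% |

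The 5% level is crossed near a ratio of 0.4, slightly below 0.5, because the assumed 58 degrees of freedom and the pooled variance also ignore the clustering. A paired t-test on patient means stays at about 5% for every split.

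**The case against.** The strongest reply is that the harm is not shown by the documents. Rho is not given, and for single-value endpoints the error is conservative, so it yields no false claim of a difference. The plan states no equivalence claim or margin. Rho could also be low for clearance in particular, because the protocol fixes blood flow, dialysate flow and ultrafiltration at the same values for all patients at the 60-minute sample. Below rho of about 0.14 a paired t-test gains nothing. All of this is fair, and it is why the size is given as a range that includes zero. It does not make an independent-samples test right for paired data, and the argument about standardised flows does not reach the endpoints measured outside that sample.

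Four limits do stand:
- Saying that a significant result survives applies only to the pairing error. It says nothing about dialyzer order, which the protocol does not state, or about multiple comparisons.
- Hemocompatibility has one session per dialyzer but several time points. The SAP does not say how these, or the pre-dialysis value, were handled. The single-value figures apply at one time point.
- The 30 v 30 analysis is a possibility, not something the SAP states. At a variance ratio of about 0.4 its type I error happens to be near nominal even though rho is positive.
- A mixed model is one choice. Paired t-tests or repeated-measures ANOVA would also respect the design.

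**Conclusion.** The concern holds. Protocol sections c and d and both appendices describe treatment of each patient with all three dialyzers; the SAP names only tests for independent groups, and nothing elsewhere repairs this.

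For one value per patient and dialyzer with positive rho, the error is conservative. At rho between 0.3 and 0.8 and n=10, the nominal 5% test runs at 2.2% down to below 0.1%, and between 9 and 37 percentage points of power are lost for a 1 SD difference (66 − 57 and 99 − 62). At rho near zero nothing is lost. For clearance and removal rate the direction is unknown until the sponsor states what was entered: with sessions treated as independent, type I error ranges from 0.1% to 19% over the variance splits shown. The clotting score loses its pairing too, and the number of scores per dialyzer needs confirming.

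These figures rest on a two-sided 5% level, normal data, equal variances and assumed correlations. That the test does not fit the design depends on none of them.

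**What to change.** Replace the SAP Methods sentence, state whether session values or patient means were used, and report the new results as a labelled re-analysis beside the original ones.

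- **Clearance and removal rate:** average the three sessions per patient and dialyzer.
- **Hemocompatibility:** use the single value per patient and dialyzer at each time point.
- **Model:** dialyzer as fixed effect and patient as random effect. Add period only if dialyzer order varied between patients; otherwise state that dialyzer and week cannot be separated.
- **Reporting:** ELISIO-H minus each comparator as a within-patient difference with 95% confidence interval. Check normality on those differences, not on the separate groups.
- **Clearly non-normal differences, and the clotting score:** Wilcoxon signed-rank or Friedman on one value per patient and dialyzer (the median if three scores exist), after reconciling the scoring frequency in Methods section g with Appendix A.

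**Cost.** No new samples are needed. The change is post hoc and must be labelled so. A single paired t-test has 9 instead of 18 degrees of freedom, which matters only below rho of about 0.14. The three-dialyzer model assumes equal correlations between dialyzers, and its type I error is slightly high (5.6%) if rho is zero.

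Missing data need care, since the protocol plans "with the expectation of a 20% drop out rate a total of twelve patients will be selected". Friedman drops a patient who lacks any dialyzer; a pairwise Wilcoxon or paired t-test drops that patient only from comparisons involving the missing one. Paired-t power for 1 SD at rho 0.5 is 88%, 80% and 68% with 12, 10 and 8 complete pairs. The mixed model keeps partial data: with 10 complete patients plus 2 who miss one dialyzer, power at rho 0.5 is 91% for the comparison those two have and 87% for one they miss, against 85% from the 10 alone.

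### The SAP names no blood-compatibility quantity or time, and its unpaired tests, if run on raw values, ignore that the same patients use all three dialyzers

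*SAP*

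**What the plan says.** SAP, Methods: "Parametric non-paired t-test was used to compare groups"; where the normality or variance test fails, "then the nonparametric Mann–Whitney Rank Sum was utilized to test for significance". No endpoint, sampling time, derived quantity, covariate or significance level is given.

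The protocol shows a within-patient design:
- Section c) Patients: "Standard hemodialysis will be performed with each dialyzer type".
- Methods, section d): "Three consecutive treatments will be performed with each dialyzer type".
- Appendix A, above the hemocompatibility table: "Sampling will be done once per patient, per dialyzer". The table marks a pre sample for WBC, platelets, Hb/Hct, C5a and TAT.
- Appendix B places this sampling mid-week ("Wednesday Compatibility Studies") and budgets blood per patient as "Total blood volume = 131.5 ml/week x 3 weeks".

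For performance, Methods section f) does define what is compared: clearance at 60 min, and removal from the 0 and 240 min samples. For hemocompatibility it only lists the markers.

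**The concern.** Hemocompatibility is one of the two things that the Evaluation Objective sets out to compare, and it rests on about 10 patients with one compatibility session per dialyzer. Precision is scarce, so two omissions matter.

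First, the quantity is open. Each marker at each time could be tested as a raw value, a change, a percentage of the pre value or an Hb-corrected value. A reader cannot tell which was done, and the power of the same test differs widely between them.

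Second, if raw values were tested, the unpaired standard error includes the differences between patients, which cancel from a within-patient comparison. The test then becomes conservative and misses real differences. In a study meant to confirm a new dialyzer against two marketed ones, a non-significant result from such a test is weak evidence of similarity.

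**Working it through.** **Layout.** Appendix B's total can be reproduced: CBC 10 + C5a 15 + TAT 22.5 = 47.5 ml; 84 + 47.5 = 131.5 ml per week; x 3 = 394.5 ml per patient. This supports one compatibility session per patient in each of three weeks. It works only with TAT tubes at all five times (5 x 4.5 = 22.5 ml), whereas Appendix A lists TAT at pre, 60 and 240 min only. Under Appendix A there are 4 (WBC) + 4 (platelets) + 4 (C5a) + 2 (TAT) = 14 on-treatment marker-times, or 14 x 3 = 42 pairwise dialyzer comparisons.

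**Inputs.** From the documents: 10 evaluable patients and 3 dialyzers. Assumed, because the documents give none: two-sided alpha 0.05; total variance of a value set to 1; share p of that variance due to patients, 0.3 to 0.8, with the same patient effect before and after; within-patient pre-post correlation r, 0.1 to 0.7; true difference 0.8 SD.

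**Step 1: the cost of ignoring pairing on raw values.** The true variance of a difference between two dialyzer means is 2(1-p)/10. The unpaired test estimates 2/10. The true standard error is therefore sqrt(1-p) of the one used: 0.84, 0.71 and 0.45 at p = 0.3, 0.5 and 0.8. Simulation under the inputs above gives:

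| Analysis | Power | False positives |
|---|---|---|
| Unpaired t-test, raw values | 33-40% | 0-3% |
| Within-patient model | 51-97% | about 5% |
| Same, with pre value as covariate | 52-100% | about 5% |

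Most of the gain over raw values comes from the within-patient model.

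**Step 2: what the unnamed quantity changes.** An unpaired test on change from pre has per-group variance 2(1-p)(1-r), against 1 for raw values. Change is the less noisy choice when r exceeds 1 - 1/(2(1-p)), which is 0.29 at p = 0.3, zero at p = 0.5, and negative at p = 0.8 (1 - 1/0.4 = -1.5). In a two-dialyzer simulation (10 patients, 0.8 SD, p = 0.5 to 0.8), the unpaired test had 34-37% power on raw values and 41-96% on change, with false-positive rates of 0.1-1% and 4-5%.

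**Step 3: what the pre value adds once the analysis is within-patient.** Residual degrees of freedom are (10-1) x (3-1) = 18. The variance ratio with v without the covariate is (1-r²) x (1 + 1/16) = 1.0625(1-r²). The confidence-interval ratio is its square root x t(17)/t(18). For plain change in the same model, the ratio to raw values is 2(1-r).

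| r | Covariate, variance | Covariate, CI width | Plain change, variance |
|---|---|---|---|
| 0.1 | 1.05 | | 1.80 |
| 0.2 | 1.02 | | 1.60 |
| 0.3 | 0.97 | 0.99 | 1.40 |
| 0.5 | 0.80 | 0.90 | 1.00 |
| 0.7 | 0.54 | 0.74 | 0.60 |

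Break-even is r = sqrt(1 - 1/1.0625) = 0.24. The largest loss, at r = 0, is 6% in variance.

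**The case against.** The strongest reply is that the stated tests do not rule out use of the pre sample. A t-test or rank-sum test can be run on change or percent of pre. If patients keep the same level before and after, change scores remove the patient effect, and the unpaired test then holds its error rate. This stands. A reader might infer that raw values were tested, or that the tests cannot adjust for the pre sample at all. The documents support neither: they show only that no such score is defined and that these tests have no covariate term.

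A reader might also infer that change scores are a poor choice whenever r is below 0.5. That holds within a within-patient model but not for the SAP's unpaired test, where the threshold is much lower (Step 2).

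The covariate itself can be challenged. The documents give no r, and at low r it costs power: in the two-dialyzer simulation at r = 0 and p = 0.5, pairing alone had 62% and pairing with the covariate 56%. Nor is the pre value a clean baseline. Sampling is on Wednesday, so if a dialyzer week starts on Monday, one treatment with the same dialyzer precedes it. Any carry-over would be partly adjusted away: a 5% shift with a slope of 0.5 moves the comparison by 1.05^0.5 = 1.025, or 2.5%. Both points stand, so the covariate should not be the only analysis.

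Finally, the SAP is written in the past tense, so nothing can now be prespecified. That also stands.

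**Conclusion.** The concern holds in this form: the blood-compatibility quantity and times are undefined; the named tests ignore the patient pairing if applied to raw values; and they can use the pre sample only through a score that the SAP does not define. Under the stated assumptions, raw unpaired testing has about 33-40% power, against 51-97% for a within-patient model. The covariate is a secondary gain: clear from about r = 0.5, neutral near 0.24, and a loss of up to about 6% in variance below that.

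A reader might go further and infer bias between dialyzers or false claims of difference. The documents show no bias, and with raw values the error runs the other way, towards missed differences. The pre-sample part covers WBC, platelets, C5a and TAT. It does not apply to the clotted-fiber score, which has no pre value. All power and variance figures rest on assumed p, r, alpha and effect size. The absence of a defined quantity needs no assumption.

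**What to change.** - For each of the four markers, name the endpoint as the log value at stated post-start times. Reconcile the TAT times between Appendices A and B.
- Compare dialyzers in a within-patient model with patient and dialyzer effects, and a period effect where the order of use allows. If every patient used the dialyzers in the same order, period and dialyzer cannot be separated, and the report should say so.
- Report the model with and without the same-session log pre value as covariate, and state before the rerun which of the two is the main result.
- Compare the pre values between dialyzers, so that any carry-over into the Wednesday sample can be seen.
- Hb/Hct correction at 240 min is an optional sensitivity analysis. It concerns 4 of the 14 marker-times.
- State which quantity and times the completed analysis used, and label the new work as a re-analysis.

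The cost is a little more analysis work, one degree of freedom for the covariate, and possible partial adjustment for carry-over. No new samples or patients are needed.

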A Clinical Study Comparing the Basic Performance and Blood Compatibility Characteristics of Nipro ELISIO-H, Gambro Polyflux Revaclear, and Fresenius Optiflux Dialyzers

> [name] MD FRCP (UK) FACP FASN Professor of Medicine (Nephrology) University of Missouri Hospitals and Clinics Columbia MO 65212 And Dialysis Clinic Incorporated Columbia, MO 65201

> > May 5, 2015

Introduction

The dialyzer ELISIO-H is a new high-flux dialyzer made from POLYNEPHRON[™] fiber designed and manufactured by Nipro Corporation Japan. The dialyzer has already been subjected to in-vitro testing, and all legally required biological safety tests have been conducted and certified by an external institute. A number of clinical studies have already been successfully completed for this membrane mainly in Japan and Europe. Nipro ELISIO-H dialyzers are commercially available for several years outside of U.S.A. On 20th December 2013, ELISIO-H dialyzer is 510k-approved for its sales in U.S.A.

Evaluation Objective

The aim of the study is to confirm the safety and clinical effectiveness of the Nipro ELISIO-H by compare the performance characteristics and hemo-compatibility of Nipro ELISIO-H with those of the commercially available dialyzers in U.S.A., Gambro Polyflux Revaclear and Fresenius Optiflux.

Clinical Investigator

[name] University of Missouri Hospitals and Clinics Columbia, MO 65212 [contact] [contact] Email: [contact]

Sponsor

Nipro Medical Corporation [name] [contact] [contact]

Principal Investigator

[name] University of Missouri Hospitals and Clinics Columbia, MO 65212 [contact] [contact] Email: [contact]

Details

a) Membrane and Dialyzer Types

Dialyzer Labelling	Membrane	Dialyzer Manufactur er	UF Coeff. mL/h/mmHg	Surface m²	Sterilization
Nipro ELISIO-H	POLYNEPHRON ™	Nipro, Japan	67.0	1.5	Gamma
Gambro Polyflux Revaclear	PAES	Gambro USA	60.0	1.4	Steam
Fresenius Optiflux	Polysulfone	Fresenius, USA	60.0	1.6	ETO

b) Design:

Study Design: Clinical study according to the US Federal Law that means no necessity of the permission of authorities, but because of blood sampling a vote of an ethics committee should be procured.

c) Patients

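### Three dialyzers are compared by two-sample tests with no stated alpha, contrasts, lead outcome or multiplicity control, so the overall false-positive rate is uncontrolled and cannot be determined

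*SAP*

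**What the plan says.** The SAP's Methods section is one sentence. The main test is given as "Parametric non-paired t-test was used to compare groups"; where a normality or variance check fails, the Mann–Whitney rank sum test "was utilized to test for significance". The SAP gives no alpha, sidedness, three-group test, list of contrasts or time points, or adjustment.

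The protocol's Evaluation Objective reads "The aim of the study is to confirm the safety and clinical effectiveness of the Nipro ELISIO-H", by comparison with two marketed dialyzers. No primary outcome is named. The outcomes are:

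- Blood Sampling, item 1: "Clearance of urea, creatinine, phosphate, beta-2-microglobulin, myoglobin at 60 min".
- Blood Sampling, item 2: removal rate "for urea, creatinine, phosphate, beta-2-m and myoglobin at 0 min and 240 min will be calculated".
- Appendix A, hemocompatibility: WBC, platelets, Hb/Hct and C5a at five times and TAT at three. "Sampling will be done once per patient, per dialyzer".
- Visual estimation of clotting: "The number of clotted capillaries in the dialyzer are counted after removal of the plastic casing", then scored 1 to 5.

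Clearance and removal are sampled at all three treatments on each dialyzer (Appendix A). Every patient uses all three dialyzers, one per week for three weeks (Patients; Dialysis Regime; Appendix B).

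**The concern.** A two-sample test can handle three dialyzers only pair by pair, so each outcome offers two or three chances of a significant result. There are also several dozen outcome/time points, and none is designated as the one that decides the study. Under an aim to confirm, any favourable or unfavourable p-value could be presented as the finding. A reader told that ELISIO-H differs from a marketed dialyzer on some marker could not tell how likely such a result was by chance, because the plan fixes neither the number of tests nor their level.

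**Working it through.** **The plan's own figure.** The documents give no alpha, power or family-wise error to reproduce. Their only sample-size arithmetic is 10 evaluable patients and 20% dropout: 10 × 1.2 = 12, as stated. (10/0.8 = 12.5 would round up to 13; this does not affect the present point.)

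**Counting the outcomes (Appendix A and the clotting section).**

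- Clearances 5; removal rates 5.
- Hemocompatibility with pre-dialysis values and Hb/Hct as one: 4 × 5 + 3 = 23. Without pre-dialysis values: 4 × 4 + 2 = 18. With Hb and Hct separate: 5 × 5 + 3 = 28, or 5 × 4 + 2 = 22 without pre-dialysis values.
- Clotting score 1.

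Lowest count: 5 + 5 + 18 = 28. Highest: 5 + 5 + 28 + 1 = 39. Two middle tallies both reach 33: 5 + 5 + 23, and 5 + 5 + 22 + 1. Appendix B also lists TAT tubes at 15 and 30 minutes; I follow Appendix A.

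**Tests at 33 points.** Two ELISIO-H contrasts: 33 × 2 = 66. All three pairs: 33 × 3 = 99.

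**If each test holds a two-sided 5% level (assumed; none is stated).**

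- Expected false positives: 99 × 0.05 = 4.95; 66 × 0.05 = 3.3. Over 28 to 39 points with three pairs: 84 × 0.05 = 4.2 to 117 × 0.05 = 5.85. At an assumed 1% level: 99 × 0.01 = 0.99.
- At least one, if independent: 1 − 0.95^99 = 99.4%; 1 − 0.95^66 = 96.6%. With a correlation of 0.5 between outcomes, simulation of 99 tests gives 84.6%.
- Per outcome, paired t-tests, n = 10, simulated: 12.6% to 12.7% over three pairs; 9.1% to 9.3% over the two ELISIO-H contrasts. Holm on those two gives 4.7% to 4.9%.

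**The test as written, one value per patient per dialyzer.** With within-patient correlation ρ, the true variance of a mean difference is 2σ²(1 − ρ)/n, but the unpaired test uses about 2σ²/n. The statistic shrinks by roughly √(1 − ρ). Simulated at n = 10 and nominal 5%:

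| Assumed ρ | Size per test | Per outcome, three pairs | Expected in 99 tests |
|---|---|---|---|
| 0 | 5.0% | 12.3% | 5.0 |
| 0.3 | 2.2% | 5.9% | 2.2 |
| 0.5 | 0.95% | 2.5% | 0.9 |
| 0.7 | 0.2% | 0.6% | 0.2 |

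The documents give no value for ρ.

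**If the three sessions are pooled as 30 values per dialyzer.** This can apply only to outcomes recorded at every treatment. With an assumed patient variance share of 0.2 to 0.3 and patient-by-dialyzer share of 0.3 to 0.4, the size per test is about 10% to 13%, and the three-pair error about 22% to 28%. Holm on two contrasts still leaves about 10% to 15%, or 17% with no patient variance and a 0.4 share. With no patient-by-dialyzer variance, pooling does not inflate: the size is 2.2% at a patient share of 0.3.

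**The case against.** A reader might infer that false significant differences are to be expected from this SAP, about 5 in 99 tests. The documents do not support that. The SAP prescribes an unpaired test on patients who serve as their own controls. With one value per patient per dialyzer and positive correlation, that test is conservative: at a correlation of about 0.5 or more, fewer than one false positive is expected in 99. The hemocompatibility values are sampled once per dialyzer, so they fall in this case. This objection stands against any unconditional count.

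It is also fair that the SAP never says all three pairs or all time points were tested, so 99 is an upper reading at 33 points. Nor does it say that sessions were pooled. The pooled figures rest on assumed variance shares and mainly reflect a separate defect that Holm does not repair. That no adjustment was made is itself inferred from silence, though in a one-sentence plan that is the natural reading.

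The objection does not establish that error is controlled. Conservatism from a mismatched test depends on an unknown correlation, could be reversed by pooling for the performance outcomes, and disappears once the analysis is correctly paired.

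**Conclusion.** The concern holds in conditional form. The plan tests for significance across three dialyzers and roughly 28 to 39 outcome/time points without stating alpha, contrasts, a lead outcome or multiplicity control, under an aim to confirm. Its overall false-positive rate is uncontrolled and cannot be determined.

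The rates of 12.6% and 9% per outcome, and of about 5 in 99 tests, apply only if each test holds an assumed 5% level, as a paired test would. They are not estimates for the unpaired test as written, whose error may be lower or higher depending on the correlation and the unit of analysis. The defect should be corrected, but it does not show that any reported difference is false.

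**What to change.** 1. Reduce the performance data to one value per patient per dialyzer (for example the mean of the three sessions) and test within patient. Holm is of little use without this step.
2. State the alpha, and name ELISIO-H v Revaclear and ELISIO-H v Optiflux as the comparisons of interest. Apply Holm to the two p-values for each outcome; per-outcome error is then about 4.7% at alpha 0.05.
3. Report Revaclear v Optiflux, and hemocompatibility time points beyond one summary per marker, descriptively and without significance claims.
4. Name one lead performance outcome for the confirmatory claim and label the others supportive. Holm within an outcome does not control error across outcomes: 5 + 5 + 6 marker summaries + 1 clotting score = 17 remain, and 1 − (1 − 0.047)^17 is about 56% if they are independent.

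**Cost.** The smaller p-value of each pair must fall below 0.025. For a paired t-test with n = 10 (9 degrees of freedom) the critical value rises from 2.262 to 2.685, so the observed mean difference must reach 2.685/√10 = 0.85 standard deviations of the differences instead of 2.262/√10 = 0.72. Some nominally significant results may be lost. No new data are needed, but the SAP is written in the past tense and dated 2019, so this means re-analysis and not just new wording. The contrasts and the lead outcome must be reported as chosen post hoc, which limits how far the result can be called confirmatory.
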